### **7.3.1 Events not considered to be a Dose-Limiting Toxicity**

#### Hematologic Toxicity

- Grade 3 or 4 neutropenia if:  
not associated with fever or systemic infection  
and  
improves by at least 1 grade within 7 days
- Grade 3 or 4 lymphopenia

#### Other Toxicity

- Grade 3 infusion-related reaction during infusion of atezolizumab, if:  
the patient did not receive corticosteroid prophylaxis  
and  
the Grade 3 reaction resolves (with appropriate clinical management) within 6 h
- Isolated Grade 3 electrolyte abnormalities if:  
not associated with clinical signs or symptoms  
and  
reversed with appropriate maximal medical intervention within 2 days
- Vitiligo or alopecia (any grade)
- Grade 3 endocrine disorder (thyroid, pituitary, and/or adrenal insufficiency), if:  
the disorder is manageable with or without systemic corticosteroid therapy and/or  
hormone replacement therapy  
and  
the patient is asymptomatic
- Grade 3 inflammatory reaction attributed to a local antitumor response (such as,  
inflammatory reaction in the lymph nodes or at sites of metastatic disease)
- Toxicity that is clearly and directly related to the primary disease or to another etiology

### **7.4 Adverse Event Reporting**

- 7.4.1 In the event of an unanticipated problem or life-threatening complications treating investigators must immediately notify the PI.
- 7.4.2 Investigators **must** report to the PI any adverse event (AE) that occurs after the initial dose of study treatment, during treatment, or within 30 days of the last dose of treatment. Serious adverse events should be reported per the guidelines in Table 26 on the MedWatch Adverse Event Reporting form.

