### 7.1 Expected Toxicities

#### 7.1.1 Abemaciclib

Most common adverse reactions (incidence  $\geq 20\%$ ) are diarrhea, neutropenia, nausea, abdominal pain, infections, fatigue, anemia, leukopenia, decreased appetite, vomiting, headache, alopecia, and thrombocytopenia.

Increases in Serum Creatinine and Renal Insufficiency:

Abemaciclib has been shown to increase serum creatinine due to inhibition of renal tubular transporters without affecting glomerular function (as measured by iohexol clearance). In clinical studies, increases in serum creatinine occurred within the first month of abemaciclib dosing, remained elevated but stable through the treatment period, were reversible upon treatment discontinuation, and were not accompanied by changes in markers of renal function, such as blood urea nitrogen (BUN), cystatin C, or calculated glomerular filtration rate based on cystatin C.

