#### **7.2.8 Adverse Event of Special Interest (AESI) for Atezolizumab**

AESIs are a subset of adverse events which may be of scientific and medical concern specific to the study drug, for which ongoing monitoring and expedited communication is required. Such an event might require further investigation in order to characterize and understand it. Depending on the nature of the event, rapid communication by the trial Sponsor to other parties (e.g., Regulatory Authorities) may also be warranted.

AESIs applicable to all participants in this trial are:

- Cases of potential drug-induced liver injury (DILI) that include an elevated ALT or AST in combination with either an elevated bilirubin or clinical jaundice, as defined by Hy's law:
  - Treatment-emergent ALT or AST  $> 3 \times$  ULN in combination with total bilirubin  $> 2 \times$  ULN
  - Treatment-emergent ALT or AST  $> 3 \times$  ULN in combination with clinical jaundice
- Suspected transmission of an infectious agent by the study drug (STIAMP), as defined below:  
Any organism, virus, or infectious particle (e.g., prion protein transmitting transmissible spongiform encephalopathy), pathogenic or non-pathogenic, is considered an infectious agent. A transmission of an infectious agent may be suspected from clinical symptoms or laboratory findings that indicate an infection in a patient exposed to a medicinal product. This term applies only when a contamination of the study drug is suspected.
- ILD/Pneumonitis

AESIs associated with participants receiving Atezolizumab:

- Systemic lupus erythematosus
- Events suggestive of hypersensitivity, infusion-related reactions, cytokine release syndrome, macrophage activating syndrome and hemophagocytic lymphohistiocytosis syndrome
- Nephritis
- Ocular toxicities (e.g., uveitis, retinitis, optic neuritis)
- Grade  $\geq 2$  cardiac disorders (e.g., atrial fibrillation, myocarditis, pericarditis)
- Vasculitis
- Autoimmune hemolytic anemia
- Severe cutaneous reactions (e.g., Stevens-Johnson syndrome, dermatitis bullous, toxic epidermal necrolysis)
- Myelitis
- Facial Paresis

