**Table 26. DF/HCC Reportable Adverse Events(AEs)**

Attribution	DF/HCC Reportable Adverse Events(AEs)				
	Gr. 2 & 3 AE Expected	Gr. 2 & 3 AE Unexpected	Gr. 4 AE Expected	Gr. 4 AE Unexpected	Gr. 5 AE Expected or Unexpected
Unrelated Unlikely	Not required	Not required	5 calendar days #	5 calendar days	24 hours*
Possible Probable Definite	Not required	5 calendar days	5 calendar days #	5 calendar days	24 hours*

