# If listed in protocol as expected and not requiring expedited reporting, event does not need to be reported.					
* For participants enrolled and actively participating in the study or for AEs occurring within 30 days of the last intervention, events must be reported within 1 business day of learning of the event.					

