## 7.5 Reporting procedures to Eli Lilly

The following are required for IIT Protocols to comply with applicable laws, regulations and standards regarding Investigator's and Institution's obligations, as the sponsor of the Study, to collect and report adverse events to regulatory authorities, IRBs, Ethics Committees or other third parties:

In addition to the obligations set forth below, Investigator and Institution agree to provide Lilly with a copy of all information Investigator and/or Institution submit to regulators related to any adverse events for the Study Drug that occur during the Study that Investigator and/or Institution have not otherwise provided Lilly; to notify Lilly, sub-investigators, and the IRB of any problems involving risk to Study patients and report new safety information to IRBs in accordance with applicable requirements; to notify Lilly within fifteen (15) business days of Investigator and/or Institution receiving notification of any "serious" adverse event experienced by a patient participating in the Study and receiving Study Drug. For purposes of this requirement, "serious" means: (1) death; (2) in-patient hospitalization or prolonged hospitalization; (3) life-threatening; (4) persistent or significant disability or incapacity; (5) congenital anomaly or birth defect; or (6) other serious events that may jeopardize the patient and may require medical or surgical intervention to prevent one of the other five listed outcomes. Serious adverse events should be reported to Lilly using a CIOMS Form or other form acceptable to Lilly. Investigator and Institution further agree to make available promptly to Lilly such records as may be necessary and pertinent for Lilly to further investigate an adverse event in the Study that is possibly associated with the Study Drug.

SAE Reporting Email Address: [mailindata\\[contact]](mailto:[contact])

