## 7.6 Reporting Procedures to Genentech

Where the patient has been exposed to atezolizumab, serious adverse events (SAEs), AEs of Special Interest (AESIs), pregnancy reports, other Special Situation Reports, and Product Complaints with or without AE, as defined above (initial and follow-up), will be reported by the Coordinating Center to Genentech Drug Safety at [usds\\[contact]](mailto:[contact]) or via [contact]) twenty-four (24) hours of awareness, via the MedWatch Adverse Event Reporting form.

All Product Complaints without an AE should call via:  
PC [contact] (M-F: 5 am to 5 pm PST)

Pregnancies will be followed up until the outcome of the pregnancy is known, whenever possible, based upon due diligence taken to obtain the follow-up information.

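### Section 7.4.2 sends SAEs to Table 26, which has no seriousness or AESI criterion, so some serious grade 2–3 events are marked as not needing a report to the sponsor

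*Combined protocol and SAP*

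**What the plan says.** Section 7.4.2 has two parts. The first obliges investigators to tell the PI about "any adverse event (AE) that occurs after the initial dose of study treatment, during treatment, or within 30 days of the last dose of treatment". The second sets the rule for serious events: "Serious adverse events should be reported per the guidelines in Table 26 on the MedWatch Adverse Event Reporting form". Section 7.4.3 says the table shows which events go to the DF/HCC Sponsor-Investigator.

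Table 26 has five columns, starting with "Gr. 2 & 3 AE Expected", and two attribution rows. Footnote #, attached to the expected grade 4 cells, reads "If listed in protocol as expected and not requiring expedited reporting, event does not need to be reported".

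Elsewhere the protocol sets duties that depend on seriousness or special interest, not on grade:

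- Sections 7.2.2 and 7.2.7.6: an adverse event leading to hospitalisation is an SAE and is reported as one, apart from listed procedural exceptions.
- Section 7.2.8: AESIs are events "for which ongoing monitoring and expedited communication is required". ILD/pneumonitis and Hy's-law liver events are AESIs in all participants.
- Section 7.5: the investigator and institution are "to notify Lilly within fifteen (15) business days" of being notified of any serious event.
- Section 7.6: in atezolizumab-exposed patients, the Coordinating Center reports SAEs and AESIs to Genentech within twenty-four "hours of awareness, via the MedWatch Adverse Event Reporting form".

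**The concern.** A site that follows 7.4.2 literally looks up an SAE in a table that never asks whether the event is serious. For several kinds of serious event the table answers that no report is needed. The later duties to Lilly and Genentech depend on someone upstream having been told.

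This matters because of where the trial stands. Combination treatment was halted after two grade 5 sepsis events among 8 Arm B patients. The Bayesian toxicity rule in 13.3 was written for combination patients, and 13.3 states no replacement rule for abemaciclib monotherapy, which continues to enrol. The DSMB meets twice a year (12.2). Prompt notice of serious, non-fatal infection is therefore an important early signal for those deciding whether enrolment should continue, and it is the notice the table leaves out.

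**Working it through.** There is no power or sample-size figure to reproduce. The check reads each cell of Table 26 against the SAE definition and the onward duties.

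**Step 1: Table 26, cell by cell**

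| Attribution | Gr 2–3 expected | Gr 2–3 unexpected | Gr 4 expected | Gr 4 unexpected | Gr 5 |
|---|---|---|---|---|---|
| Unrelated, unlikely | none | none | 5 days (#) | 5 days | 24 h |
| Possible, probable, definite | none | 5 days | 5 days (#) | 5 days | 24 h |

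Of 2 × 5 = 10 cells, 3 require no report, 5 allow 5 calendar days (2 of them subject to #) and 2 say 24 hours (footnoted as one business day). Of the four grade 2–3 cells, 3 require no report. There is no grade 1 column and no row or column for seriousness or AESI.

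**Step 2: a worked case.** An abemaciclib patient is hospitalised with a grade 3 infection that is not life-threatening.

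- Under 7.2.2 and 7.2.7.6 it is an SAE, to be reported as such.
- Section 7.1.1 lists infections among the common abemaciclib reactions ("diarrhea, neutropenia, nausea, abdominal pain, infections, fatigue, anemia"). Formal expectedness rests on the package insert or Investigator's Brochure (7.2.6), which are not in the documents, so both branches are needed:
  - expected, any attribution: no report;
  - unexpected, unrelated or unlikely: no report;
  - unexpected, possibly to definitely related: 5 calendar days.

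**Step 3: onward duties and whom they cover**

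| Section | Event | Patients | Clock |
|---|---|---|---|
| 7.2.7.6 | hospitalised AE | all | none stated |
| 7.2.8 | AESI | all for three categories, atezolizumab-exposed for the rest | expedited, no figure |
| 7.5 | any serious event | receiving study drug, read here as abemaciclib: 27 + 8 + 16 = 51 | 15 business days from notification |
| 7.6 | SAE or AESI | atezolizumab-exposed: 8 + 5 = 13 | 24 hours from awareness |

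None of these is limited by grade or expectedness. Patients on abemaciclib alone number up to 27 + 16 = 43, and 7.6 does not apply to them.

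**Step 4: clauses that might close the gap**

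- Sections 7.2.3, 7.4.2 (first sentence), 7.8 and Appendix B-2.2 all require reporting. None gives a deadline in hours or days, and 7.8 is routine data submission.
- Section 7.4.1 requires immediate notice to the PI of unanticipated problems and life-threatening complications.
- Table 21 requires Sponsor-Investigator contact for grade 2–4 ILD/pneumonitis. Table 5 does so for grade 3–4 pulmonary events.
- Table 22 requires it for grade 2–3 transaminase rises with bilirubin above 2 × ULN without cholestasis, and for grade 4 rises.

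What remains is mainly the serious but not life-threatening event outside the lung and liver rules, with infection the clearest case. Grade 1 pneumonitis is also left: 7.2.8 sets no grade limit, but neither Table 26 nor the grade 1 row of Table 21 calls for sponsor contact.

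**Step 5: the timed cells.** Five calendar days is up to 5 × 24 = 120 hours. Section 7.6 does not say whose awareness starts its 24 hours. If it is the Coordinating Center's, 120 hours at the site does not breach it; if it is the site's, it does.

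**The case against.** The strongest reply is that these events are still reportable. Section 7.4.2 opens by requiring any adverse event to go to the PI, 7.2.3 covers all AEs and SAEs, and B-2.2 tells external sites to submit SAE reports. Sites and the Coordinating Center also confer about monthly (B-4.1). This stands, and it rules out several stronger readings:

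- A reader might infer that the duties in 7.6 and 7.2.8 cannot be met. They can, because untimed reporting duties exist and 7.6 runs from awareness. What is missing is a timed step from site to sponsor.
- A reader might infer that the Sponsor-Investigator hears of these events only through case report forms. Tables 5, 21 and 22 and section 7.4.1 contradict that for grade 2–4 pneumonitis, the liver pattern and life-threatening events.
- A reader might apply the 24-hour clock to every patient. Section 7.6 is confined to atezolizumab exposure.
- A reader might cite Table 25 as making every grade 4 event an SAE. That table covers only events not listed in CTCAE.

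Two further points are fair. A hospitalised grade 3 infection may be unexpected in severity, and 7.2.5 calls for expedited reporting when a listed event departs from the expected information. That moves some related cases to the 5-day cell but leaves the rest exempt. Footnote # needs two conditions, and no list of events excluded from expedited reporting appears in the available text, so it may exempt nothing in practice.

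B-2.2 does not settle the matter. It asks for SAE reports according to DF/HCC requirements, and the only such schedule in the documents is Table 26. DF/HCC policies, and some text next to 7.6, were not available to check.

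**Conclusion.** The point holds as an internal contradiction in a stated reporting rule. Followed literally, 7.4.2 with Table 26 exempts serious grade 2–3 events in 3 of 4 cells, while 7.2.7.6, 7.2.8, 7.5 and, for the 13 atezolizumab-exposed patients, 7.6 require them to be reported or passed on. Timely notice from site to sponsor is therefore not assured. It is not impossible.

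The practical weight falls on serious, non-life-threatening events such as infection in up to 43 patients on abemaciclib alone, for whom the onward duties are 7.5 and the all-participant AESIs in 7.2.8. The documents do not allow an estimate of how many events would be delayed: the 20% threshold in 7.1.1 concerns reactions of any severity, not serious grade 2–3 events. The infection example assumes the event is classed as expected, or as unexpected but unrelated or unlikely.

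**What to change.** Reconcile section 7.4.2 and Table 26 with 7.2.2, 7.2.7.6, 7.2.8, 7.5 and 7.6 in the next amendment:

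1. Add an overriding first row to Table 26: any event meeting 7.2.2 (SAE) or listed in 7.2.8 (AESI) is reported by the site to the Sponsor-Investigator and Coordinating Center, whatever its grade, expectedness or attribution.
2. State the deadline and whose awareness starts it. It must be short enough for the onward duties. Twenty-four hours would match 7.6 for atezolizumab-exposed patients; the sponsor may set the clock for abemaciclib-only patients, whose onward figure in 7.5 is 15 business days.
3. Keep the existing grid for non-serious events only.
4. State that footnote # does not apply to SAEs or AESIs.

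The cost is one row, one footnote and a modest rise in expedited site reports for events that 7.8 already collects. Treatment, sample size and analysis are unchanged.

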#### 7.4.3 Adverse Event Reporting Guidelines

All participating sites will report AEs to the Sponsor-Investigator per DF/HCC

requirements, and the IRB of record for each site as applicable per IRB policies. The table below indicates which events must be reported to the DF/HCC Sponsor-Investigator.

**Table 26. DF/HCC Reportable Adverse Events(AEs)**

Attribution	DF/HCC Reportable Adverse Events(AEs)				
	Gr. 2 & 3 AE Expected	Gr. 2 & 3 AE Unexpected	Gr. 4 AE Expected	Gr. 4 AE Unexpected	Gr. 5 AE Expected or Unexpected
Unrelated Unlikely	Not required	Not required	5 calendar days #	5 calendar days	24 hours*
Possible Probable Definite	Not required	5 calendar days	5 calendar days #	5 calendar days	24 hours*
# If listed in protocol as expected and not requiring expedited reporting, event does not need to be reported.					
* For participants enrolled and actively participating in the study or for AEs occurring within 30 days of the last intervention, events must be reported within 1 business day of learning of the event.					

## 7.5 Reporting procedures to Eli Lilly

The following are required for IIT Protocols to comply with applicable laws, regulations and standards regarding Investigator's and Institution's obligations, as the sponsor of the Study, to collect and report adverse events to regulatory authorities, IRBs, Ethics Committees or other third parties:

In addition to the obligations set forth below, Investigator and Institution agree to provide Lilly with a copy of all information Investigator and/or Institution submit to regulators related to any adverse events for the Study Drug that occur during the Study that Investigator and/or Institution have not otherwise provided Lilly; to notify Lilly, sub-investigators, and the IRB of any problems involving risk to Study patients and report new safety information to IRBs in accordance with applicable requirements; to notify Lilly within fifteen (15) business days of Investigator and/or Institution receiving notification of any "serious" adverse event experienced by a patient participating in the Study and receiving Study Drug. For purposes of this requirement, "serious" means: (1) death; (2) in-patient hospitalization or prolonged hospitalization; (3) life-threatening; (4) persistent or significant disability or incapacity; (5) congenital anomaly or birth defect; or (6) other serious events that may jeopardize the patient and may require medical or surgical intervention to prevent one of the other five listed outcomes. Serious adverse events should be reported to Lilly using a CIOMS Form or other form acceptable to Lilly. Investigator and Institution further agree to make available promptly to Lilly such records as may be necessary and pertinent for Lilly to further investigate an adverse event in the Study that is possibly associated with the Study Drug.

SAE Reporting Email Address: [mailindata\\[contact]](mailto:[contact])

## 7.6 Reporting Procedures to Genentech

Where the patient has been exposed to atezolizumab, serious adverse events (SAEs), AEs of Special Interest (AESIs), pregnancy reports, other Special Situation Reports, and Product Complaints with or without AE, as defined above (initial and follow-up), will be reported by the Coordinating Center to Genentech Drug Safety at [usds\\[contact]](mailto:[contact]) or via [contact]) twenty-four (24) hours of awareness, via the MedWatch Adverse Event Reporting form.

All Product Complaints without an AE should call via:  
PC [contact] (M-F: 5 am to 5 pm PST)

Pregnancies will be followed up until the outcome of the pregnancy is known, whenever possible, based upon due diligence taken to obtain the follow-up information.

**For questions related to safety reporting, please contact Genentech Drug Safety:**

[contact]

[contact] or [contact]

*Reporting to Regulatory Authorities, Ethics Committees and Investigators*

The Sponsor-Investigator will be responsible for the expedited reporting of safety reports originating from the Study to the Independent Ethics Committees/ Institutional Review Boards (IEC/IRB) of the Concerned Member States, where applicable.

The Sponsor-Investigator will be responsible for the distribution of safety information to its own investigators, where relevant, in accordance with local regulations.

And the Sponsor-Investigator will be responsible for the distribution of safety information to Site IRB: [contact].

For questions related to safety reporting, please contact Genentech Drug Safety:

[contact]

[contact] or [contact]

### MedWatch 3500A Reporting Guidelines

In addition to completing appropriate patient demographic (Section A) and suspect medication information (Sections C & D), the report should include the following information within the Event Description (Section B.5) of the MedWatch 3500A form:

- Protocol number and title description

- Description of event, severity, treatment, and outcome if known
- Supportive laboratory results and diagnostics (Section B.6)
- Investigator's assessment of the relationship of the adverse event to each investigational product and suspect medication

## **Follow-Up Information**

Additional information may be added to a previously submitted report by any of the following methods:

- Adding to the original MedWatch 3500A report and submitting it as follow-up
- Adding supplemental summary information and submitting it as follow-up with the original MedWatch 3500A form
- Summarizing new information and faxing it with a cover letter including patient identifiers (i.e., D.O.B., initials, patient number), protocol description and number, if assigned, brief adverse event description, and notation that additional or follow-up information is being submitted (The patient identifiers are important so that the new information is added to the correct initial report)

MedWatch 3500A (Mandatory Reporting) form is available at

<https://www.fda.gov/media/69876/download>

### **7.6.1 Case Transmission Verification of Single Case Reports**

The Sponsor agrees to conduct the Case Transmission verification to ensure that all single case reports have been adequately received by Genentech via Investigator-Sponsor emailing Genentech a Quarterly line-listing documenting single case reports sent by Investigator-Sponsor to Genentech in the preceding time period.

The periodic line-listing will be exchanged within seven (7) calendar days of the end of the agreed time period. Confirmation of receipt should be received within the time period mutually agreed upon.

If discrepancies are identified, the Sponsor and Genentech will cooperate in resolving the discrepancies. The responsible individuals for each party shall handle the matter on a case-by-case basis until satisfactory resolution. The sponsor shall receive reconciliation guidance documents within the 'Activation Package'.

Following Case Transmission Verification, single case reports which have not been received by Genentech shall be forwarded by Investigator-Sponsor to Genentech within five (5) calendar days from request by Genentech.

At the end of the study, a final cumulative Case Transmission Verification report will be sent to

Genentech.

